The gold standard for a diagnosis of EILO is a continuous laryngoscopy exercise (CLE) test, in which a flexible endoscope is used to monitor the laryngeal movement in real-time during exercise (Hall, et al., 2016). The tip of the endoscope is positioned in the mesopharynx (identified in Figure 1) by the clinician, who uses the live image from the endoscope to guide its position. A securing headgear is essential to keep the endoscope in a fixed position while the patient exercises, both to achieve a stable image and for the safety of the patient. An example of a CLE test set-up is displayed in Figure 2. This method of investigation is not currently offered by LUHFT, and other centres we have contacted provide the service using a non-CE/UKCA marked headgear.

[figure not shown]

Figure 1: showing the location of the mesopharynx, taken from (James F. Bosma M.D., 1986)

[figure not shown]

Figure 2: Continuous laryngoscopy exercise (CLE) test (Hall, et al., 2016)

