6.2 Primary and Secondary Endpoints/Outcome Measures

6.2.1 Primary Outcome Measure

Device effectiveness, measured by the proportion of CLE tests where the endoscopy image was clear and stable enough to allow a diagnosis of EILO to be confirmed or ruled out.

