6.4.4 Subsequent assessments

Following the consultation appointment, the participant will attend one investigation appointment to undergo the CLE test on-site at the Outpatient Department, Alexandra Wing, Broadgreen Hospital. There will be no follow-up assessments.

On the day of the investigation appointment, the Principal Investigator will address any questions or concerns before the investigation begins. If the participant still wishes to partake in the study, signed consent will be obtained from the participant. The right of the participant to refuse to participate without giving reasons will be respected. After the participant has entered the study the clinician remains free to give alternative treatment to that specified in the protocol at any stage if he/she feels it is in the participant's best interest, but the reasons

for doing so should be recorded. In these cases, the participants remain within the study for the purposes of data analysis.

Eligibility will be reviewed for any changes, ensuring that the participant meets the inclusion criteria and none of the exclusion criteria apply. As part of this, the circumference of the participant's head around the forehead will be measured and recorded. Signed consent will then be obtained. The participant will then undergo the CLE test following standard clinical practice.

The order of events of the aspects of the investigation related to the headgear will be:

1. The headgear is prepared for use.
2. The headgear is fitted onto the participant's head.
3. The endoscope is inserted into the participant.
4. The endoscope is fitted onto the headgear.
5. The CLE test is carried out.
6. The endoscope is removed from the headgear.
7. The endoscope is removed from the participant.
8. The headgear is removed from the participant.
9. The headgear is cleaned and stored.

Following completion of the CLE test, the participant will complete a questionnaire:

- How tolerable was the headgear during the investigation?
 - 1) Highly intolerable
 - 2) Intolerable
 - 3) Tolerable
 - 4) Highly tolerable
- Please tell us any concerns about the headgear, thinking about how comfortable it was, how hot your head felt, the weight of the headgear, how secure it felt and the impact of the headgear on your performance during the investigation.

Following the appointment, the clinician will complete a questionnaire including:

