- Was the endoscopy image clear and stable enough to allow a diagnosis of EILO to be confirmed or ruled out? (Note that participants are withdrawn from the study if the

CLE test is unable to allow a diagnosis of EILO to be confirmed or ruled out due to reasons unrelated to the headgear.)

- How easy was it to use the headgear?

- 1) Very hard to use;
- 2) Hard to use;
- 3) Neither hard nor easy to use;
- 4) Easy to use;
- 5) Very easy to use.

- Please record any concerns about the headgear, thinking particularly about set-up, operation and cleaning.

Data will be handled as detailed in Section 13 Data Handling and Record Keeping.

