6.5 Discontinuation/ Withdrawal of Participants from Study Treatment

Each participant has the right to withdraw study at any time. In addition, the investigator may discontinue a participant from the study at any time if the investigator considers it necessary for any reason including:

- Pregnancy
- Ineligibility (either arising during the study or retrospective having been overlooked at screening)
- Significant protocol deviation
- Significant non-compliance with study requirements
- An adverse event, adverse device effect, serious adverse device effect or unanticipated adverse device effect which results in cessation of the CLE test or inability to continue to comply with study procedures
- Consent withdrawn
- If the participant cannot wear the headgear, e.g. it does not fit.
- If the CLE test is unable to allow a diagnosis of EILO to be confirmed or ruled out due to reasons unrelated to the headgear, e.g. the participant cannot tolerate the endoscopy.

Withdrawn participants will be replaced.

The reason for withdrawal will be recorded in the Case Report Form (CRF).

If the participant is withdrawn due to an adverse event, the investigator will arrange for follow-up visits or telephone calls until the adverse event has resolved or stabilised.

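### The untimed example 'cannot tolerate the endoscopy' in section 6.5 can let headgear-caused failures leave the primary denominator once the endoscope is fixed to the headgear

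*Combined protocol and SAP*

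**What the plan says.** The primary outcome (6.2.1) is "measured by the proportion of CLE tests where the endoscopy image was clear and stable enough to allow a diagnosis of EILO", whether the finding is positive or negative. Section 9.1 compares it with a reference of 49 in 50.

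Section 6.5 says "the investigator may discontinue a participant from the study at any time if the investigator considers it necessary". The last ground in its list is a non-diagnostic test "due to reasons unrelated to the headgear, e.g. the participant cannot tolerate the endoscopy". That is the only example given for this ground, and it does not say when in the procedure the intolerance must arise. The section then states: "Withdrawn participants will be replaced". The reason for withdrawal goes in the CRF.

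The note in 6.4.4 repeats the rule beside the primary-outcome question on the clinician's questionnaire. There it is unconditional: participants are withdrawn if the "CLE test is unable to allow a diagnosis of EILO to be confirmed or ruled out due to reasons unrelated to the headgear".

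The order of events in 6.4.4 has "The headgear is fitted onto the participant's head" at step 2, insertion of the endoscope at step 3, "The endoscope is fitted onto the headgear" at step 4, and the CLE test at step 5. Section 4.2 says the headgear is needed to hold the endoscope in place during exercise, "both to achieve a stable image and for the safety of the patient". Section 7.1 describes a front clamp on a 1.5 kg helmet.

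Section 9.7 puts all eligible participants in the analysis and does not mention withdrawn ones.

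**The concern.** Before step 4 the headgear is not holding the endoscope, so intolerance at insertion is unlikely to reflect how well it holds. From step 4 the headgear does hold it, in a patient who then exercises. If it holds badly, the endoscope may move, and a patient may be unable to bear that. Such a test fails because of the device, yet the protocol's example points towards calling it unrelated.

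The timing of the decision adds to the problem. This ground applies only when the test has already proved non-diagnostic, so the choice between counting a failure and replacing the participant is always made with the result known. Neither section says who judges relatedness or by what criteria. Recording a reason such as intolerance of the endoscope would not separate a stop at step 3 from one at step 5.

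At stake are the estimated success proportion, its interval, and the ability to detect that the headgear falls short of 98%.

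**Working it through.** **Inputs from the documents.** n = 30 (9.2); reference p0 = 49/50 = 0.98, so the reference failure rate is 0.02 (9.1), which agrees with the stated limit of 1 in 50; significance level 0.01, sidedness not stated (9.3). There is no power calculation to reproduce, because 30 was chosen for practical reasons.

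**Not in the documents.** The rate of endoscopy intolerance from step 4 onward, and the share of it caused by the headgear. Both are varied below.

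**1. Can the study show success?** In the best case, 30/30, the exact upper-tail p is 0.98^30 = 0.545. Significance at one-sided 0.01 would need ln(0.01)/ln(0.98) = 227.9, that is 228 consecutive successes. The classification rule therefore cannot create or remove a significant success claim.

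**2. Effect of w replaced stops.** Suppose all 30 analysed tests succeed and w stops from step 4 onward were replaced. Counted as failures, the proportion is 30/(30 + w). The exact p is P(at least w failures in 30 + w tests at failure rate 0.02), treating the number tested as fixed.

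| w | Proportion | Exact p for a shortfall |
|---|---|---|
| 0 | 30/30 = 100% | 1 |
| 1 | 30/31 = 96.8% | 0.465 |
| 2 | 30/32 = 93.8% | 0.134 |
| 3 | 30/33 = 90.9% | 0.028 |
| 4 | 30/34 = 88.2% | 0.0046 |

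The two-sided exact p values are the same for these rows. One stop takes the estimate below 98%. That is partly a matter of sample size, since any single failure in 30 does so (29/30 = 96.7%). Four are needed before the shortfall is significant at 0.01. The same holds with n fixed at 30: at least 3 failures has probability 0.022 and at least 4 has 0.0029.

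**3. Assumed range.** Let f be the true device failure rate and s the share of those failures classed as endoscopy intolerance and replaced. The observed failure rate is f(1 − s)/(1 − fs). Expected replacements are 30/(1 − fs) − 30. For f = 0.10 and s = 0.5, the observed rate is 0.05/0.95 = 0.053, so success is 94.7%, with 30/0.95 − 30 = 1.6 replacements.

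| f | s | Observed success | Chance of at least 4 counted failures in 30 | Expected replacements |
|---|---|---|---|---|
| 5% | 0 | 95.0% | 6.1% | 0 |
| 5% | 50% | 97.4% | 0.7% | 0.8 |
| 5% | 100% | 100% | 0% | 1.6 |
| 10% | 0 | 90.0% | 35.3% | 0 |
| 10% | 25% | 92.3% | 19.6% | 0.8 |
| 10% | 50% | 94.7% | 7.1% | 1.6 |
| 10% | 75% | 97.3% | 0.8% | 2.4 |
| 10% | 100% | 100% | 0% | 3.3 |

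With a true failure rate of 10%, reclassifying half the failures cuts the chance of a significant shortfall from 35% to 7%, at a cost of one or two replacements.

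**The case against.** **The governing words still require a reason unrelated to the headgear.** This stands. Intolerance caused by a slipping clamp falls outside the ground on its own terms, and 6.5 is permissive. A reader might infer that device failures do leave the denominator. The documents support only that they can, if the example is followed. The example is nonetheless the only guidance given, and the note in 6.4.4 is not permissive.

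**The mechanism is not in the documents.** This also stands. It is inferred from the step order, the clamp and the headgear's stated function. But the human testing described in 9.2 was done without an inserted endoscope, so nothing in the documents supports presuming unrelatedness either.

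**Removal from the analysis is not stated.** Partly right. It is the natural reading of withdrawal with replacement, but 9.7 could be read otherwise. That is a reason to reconcile the sections.

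**Counting all later intolerance as failure would bias the result the other way.** This stands against a rigid step-4 cut-off. Exercise starts at step 5, and section 4.1 says EILO itself can bring fear, panic and pain. An exception limited to causes already present before step 4 could never cover these.

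**Other safeguards exist.** Withdrawal reasons are recorded and adverse events are reported whatever their attribution (8.2). Neither puts a case back into the primary proportion. The tolerability item rates the headgear and follows completion of the test, so it does not do so either.

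**Conclusion.** The point holds as a classification gap that should be closed. Followed as written, the example can move headgear-caused failures out of the 98% comparison after the result is known, and replacement conceals the loss in the reported 30.

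One reclassified stop can separate a reported 100% from 96.8%. Four can separate it from a shortfall significant at 0.01. These figures assume that the other 30 tests all succeed and that the stops were device failures. The true number may be zero.

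A reader might infer that the rule could produce a false finding of success. It cannot, because 30/30 does not reach significance against 98%. The damage is to the estimate, its interval and the detection of a shortfall. A reader might also infer that all endoscopy intolerance should count against the device. The documents do not support that: intolerance at insertion, or from a cause that first arises in exercise, may be unrelated.

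**What to change.** These changes concern how a stopped test is counted, not how the patient is managed.

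1. In 6.5 and the 6.4.4 note, limit the intolerance example to intolerance arising before step 4.
2. Where intolerance from step 4 onward leaves the test non-diagnostic, keep the test in the denominator as a failure by default. Allow an exception when the CRF documents a specific cause unrelated to the headgear, including one that first arises during exercise.
3. Record on the CRF the step at which each test stopped.
4. Report all withdrawals by reason and step, with a sensitivity analysis counting every withdrawal from step 4 onward as a failure.
5. Apply the same denominator rule when the stop is recorded under the adverse-device-effect ground in 6.5. Otherwise the same participant could still be withdrawn and replaced by that route.
6. Reconcile 6.4.4 and 6.5 with 9.7, including the permissive and unconditional wordings of the withdrawal rule.

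The cost is a few sentences of protocol text, one CRF field and one extra analysis. Some intolerance not caused by the headgear may count against it, making the estimate somewhat pessimistic. At n = 30 one such case moves the point estimate below 98%, but four are needed for a significant shortfall at 0.01.

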6.6 Source Data

Source documents are original documents, data, and records from which participants' CRF data are obtained. These include, but are not limited to, hospital records (from which medical history and previous and concurrent medication may be summarised into the CRF), clinical and office charts, Device, laboratory and pharmacy records, diaries, microfiches, radiographs, and correspondence.

CRF entries will be considered source data if the CRF is the site of the original recording (e.g., there is no other written or electronic record of data). In this study the CRF will be used as the source document for the participant head circumference, the participant questionnaire results, and the clinician questionnaire results.

All documents will be stored safely in confidential conditions. On all study-specific documents, other than the signed consent, the participant will be referred to by the study participant number/code, not by name.

7. TREATMENT OF TRIAL PARTICIPANTS

7.1 Description of Study Intervention(s)

Two headgears of the same design will be manufactured. The headgear is constructed from a modified safety helmet with a clamp fixed on the front to hold the endoscope, and a counterweight fixed on the back for comfort and stability.

A label will be attached indicating that the device is for use in the HALOS pilot study only by trained individuals. User instructions and training will be provided.

Headgear properties:

- Components:
 - White Hard Hat with Chin Strap (ABS, High-Strength Polyester, Nylon, Polycarbonate, Polyethylene)
 - Clamp (Aluminum)
 - Clamp mount (Steel)
 - Secondary fixture (Steel)

- Endoscope strap (Velcro)
- Chin strap (Velcro)
- Counterweight (steel).
- Weight: 1.5 kg

Below are photos of the HALOS headgear device placed on a dummy head with and without the endoscope inserted.

[figure not shown]

Figure 3: A labelled diagram of the HALOS headgear positioned on a dummy head

Figure 5: A front view of the HALOS headgear positioned on a dummy head

Figure 5: A top view of the HALOS headgear

[figure not shown]

Figure 6: The HALOS headgear with the endoscope inserted positioned on a dummy head, showing views from (a) left side, (b) right side, (c) front, (d) top, (e) back

7.2 Maintenance and storage of device

The two headgear devices will be stored on-site at Broadgreen Hospital, LUHFT, in warm and dry conditions.

After each participant use, the headgear will be thoroughly wiped with disinfectant wipes, and removable fabric straps will be washed with soap and water. Cleaning events will be recorded.

The Velcro strap used to secure the endoscope on the front of the headgear is single-use, and to be disposed of after each participant assessment.

7.3 Risk Management

Device risks are managed by following the Department of Medical Physics and Clinical Engineering Quality Management System, which complies with ISO 14971:2012 Medical

devices – Application of risk management to medical devices. A Risk Management Plan and Risk Assessment are in use.

8. SAFETY REPORTING

8.1 Definitions³

8.1.1 Device Deficiency (DD)

This is the inadequacy of a medical device with respect to its identity, quality, durability, reliability, usability, safety or performance. Device deficiencies include malfunction, use error and inadequate labelling.

8.1.2 Adverse Event (AE)

Any untoward medical occurrence, unintended disease or injury or any untoward clinical signs (including an abnormal laboratory finding) in subjects, users or other persons, whether or not related to the investigational medical device and whether anticipated or unanticipated.

This includes events related to the investigational device or the comparator and events related to the procedures involved (any procedure in the study protocol). For users or other persons, i.e. where the medical occurrence, unintended disease or injury is not in the subject, this definition is restricted to events related to the use of investigational medical devices or comparators.

No potential AEs are identified.

The categories of adverse events are shown in Table 1.

³ Source: BS EN ISO 14155:2020 Clinical Investigation of Medical Devices for Human Subjects – Good Clinical Practice.

Table 1: Categories of adverse events (taken from BS EN ISO 14155:2020 Table F.1)

Adverse events	Non-device-related	Device- or investigational procedure-related	
Non-serious	Adverse event (AE) ^a (3.2)	Adverse device effect (ADE) ^c (3.1)	
Serious	Serious adverse event (SAE) ^b (3.45)	Serious adverse device effect (SADE) (3.44)	
		Anticipated	Unanticipated
		Anticipated serious adverse device effect (ASADE) ^c (3.1, Note 1 to entry)	Unanticipated serious adverse device effect (USADE) (3.51)

^a Includes all categories.
^b Includes all categories that are serious.
^c Includes all categories that are related to the device or the investigational procedure.

8.1.3 Serious Adverse Event (SAE):

SAE is an adverse event that led to any of the following:

- death
- foetal distress, foetal death or congenital abnormality or birth defect including physical or mental impairment.
- serious deterioration in the health of the subject, users or other persons as defined by one or more of the following:
 - a life-threatening illness or injury
 - a permanent impairment of a body structure or a body function including chronic diseases
 - in-patient or prolonged hospitalisation
 - medical or surgical intervention to prevent life-threatening illness or injury, or permanent impairment to a body structure or a body function

Planned hospitalisation for a pre-existing condition, or a procedure required by the Study Protocol, without serious deterioration in health, is not considered a serious adverse event.

8.1.4 Adverse Device Effect (ADE)

Adverse event related to the use of an investigation medical device. This includes AEs resulting from insufficient or inadequate instructions for use, deployment, implantation, installation, or operation, or any malfunction of the investigational medical device. This includes the comparator if the comparator is a medical device.

All AEs judged by either the reporting medically qualified professional or the sponsor as having a reasonable suspected causal relationship to the device qualify as ADEs. For guidance on causality assessment, refer to MEDDEV 2.7/3 Clinical Investigations: Serious Adverse Event Reporting Under Directive 90/385/EEC and 93/42/EEC.

8.1.5 Serious Adverse Device Effects (SADE):

Adverse device effect that has resulted in any of the consequences of a serious adverse event.

All cases judged by either the reporting medically qualified professional or the sponsor.

8.1.6 Unanticipated Serious Adverse Device Effect (USADE):

Any serious adverse device effect which by its nature, incidence, severity or outcome has not been identified in the current risk assessment.

8.2 Reporting of AEs

All AEs occurring during the study observed by the investigator or reported by the participant, whether or not attributed to the device under investigation, will be reported, without undue delay, to the Chief Investigator and LUHFT R&D and recorded on the hospital incident reporting system, in the source data (medical notes) and the CRF. Any questions concerning adverse event reporting should be directed to the Chief Investigator in the first instance.

8.3 Reporting of DDs/SAEs/SADEs/USADEs

All SAEs, SADEs, and USADEs will be reported to the sponsor/legal representative, Chief Investigator and LUHFT R&D **immediately**; regardless of relationship to the device. DDs that might have led to an SADE if suitable action had not been taken, intervention had not been made or if circumstances had been less fortunate are similarly reported. All SAEs, SADEs and USADEs will be recorded on the hospital incident reporting system, in the source data (medical notes) and the CRF.

Reports of related and unexpected SAEs should be submitted to the Research Ethics Committee (REC) within 15 days of the Chief Investigator becoming aware of the event, using the SAE report form for non-CTIMPs published on the HRA website⁴.

All reporting to LUHFT R&D should be by email to [contact] giving as much information about the incident as possible, and should be signed by the PI or Co-investigator. The LUHFT SADE reporting form should be used for LUHFT sponsored studies.

The LUHFT R&D Department will undertake an initial review of the information and ensure it is reviewed. Events will be followed up until resolution, any appropriate further information will be sent by the research team in a timely manner.

8.4 Safety Reports

In addition to the above reporting the Chief Investigator will submit on request a progress/safety report to the REC and R&D.

9. STATISTICS

9.1 Description of Statistical Methods

A single proportion test will be applied to the primary outcome measure (see Section 6.2.1), using a reference proportion of 49 in 50. This is derived from a clinical estimate of the threshold for acceptable performance of the headgear being where the resulting endoscopy image is not sufficiently clear and stable in no more than 1 in 50 cases.

The secondary outcome measures (see Section 6.2.2) will be used as follows:

- The device usability and tolerability ratings will be used to support the risk/benefit ratio assessment of the device.
- Device usability and tolerability subjective feedback will be used to inform and prioritise how residual risks associated with usability and tolerability can be reduced.

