4.4 Rationale for Current Study

A headgear is necessary to carry out CLE tests for the investigations of EILO, as the endoscope must be kept stable for both image quality and patient safety. There is no commercial option existing on the market at present, and other centres have manufactured their headgear in-house (Liverpool Heart and Chest Hospital (LHCH), Royal Brompton Hospital).

Without a specialised headgear it is not possible to carry out CLE tests at LUHFT, and patients are sent for investigations at LHCH. This study is an essential step in improving the care that can be offered by LUHFT for sufferers of EILO. Evaluating the in-house design of headgear is necessary to support its safe and effective clinical use in accordance with the Medical Device Directive (MDD) 93/42 and in the spirit of the European Medical Device Regulations (MDR) 2017/745. By producing an in-house manufactured headgear, it will enable LUHFT to provide an additional service for patients, avoiding the inconvenience to them of having to travel further afield.

Therefore, the hypothesis for this study is that the HALOS headgear is sufficiently effective for clinical use, and that the risks are understood adequately for an accurate benefit/risk ratio evaluation.

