9.2 The Number of Participants

The number of participants is limited to 30 for practical reasons, based on the expected rate that participants can be recruited.

The following rationale was applied to determine this as an acceptable number of samples:

⁴ <https://www.hra.nhs.uk/approvals-amendments/managing-your-approval/safety-reporting/>, accessed 16/Aug/2021

- This is a Class I (MDD), low-risk device, and risk management according to ISO 14971 has been used to predict a favourable overall risk/benefit ratio.
- Bench testing has been carried out to verify that the design meets the specifications.
- Limited validation of the headgear has been carried out to partially show that the device is fit for purpose. This included testing on humans but without the endoscope inserted into them. The results demonstrated to a large extent that the design is safe and effective.

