9.3 The Level of Statistical Significance

A conservative level of significance of $p=0.01$ will be used to control the false discovery rate, due to the expected small limiting sample size (Harrell, 2015).

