16. PUBLICATION POLICY

An internal report will be produced detailing the findings from the study in the form of a clinical evaluation in line with MEDDEV 2.7/1 Clinical Evaluation: A Guide for Manufacturers. The study will also be used to update the Risk Log for the device.

Although the main reason for this Study is it to enable LUHFT to provide an additional service for patients, publication in a peer reviewed scientific journal or as a report on our website will be considered to disseminate the findings of this study to interested parties.

Authors will be defined as those who have made:

- Substantial contributions to the conception or design of the work; or the acquisition, analysis, or interpretation of data for the work; **AND**
- Drafting the work or revising it critically for important intellectual content; **AND**
- Final approval of the version to be published; **AND**
- Agreement to be accountable for all aspects of the work in ensuring that questions related to the accuracy or integrity of any part of the work are appropriately investigated and resolved.

Contributors who have contributed materially to the paper but whose contributions do not justify authorship will be described clearly in acknowledgements.

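### With 30 participants the primary test against 49/50 at 0.01 cannot show that the headgear meets the 1-in-50 limit, and the plan gives no direction, method or pass rule

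*Combined protocol and SAP*

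**What the plan says.** Section 6.2.1 defines the primary outcome as how effective the device is, "measured by the proportion of CLE tests where the endoscopy image was clear and stable enough to allow a diagnosis of EILO", whether positive or negative. Section 9.1 gives the only analysis of it: "A single proportion test will be applied to the primary outcome measure (see Section 6.2.1), using a reference proportion of 49 in 50". The reference comes from a clinical judgement that performance is acceptable when "the resulting endoscopy image is not sufficiently clear and stable in no more than 1 in 50 cases".

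On sample size, section 9.2 says: "The number of participants is limited to 30 for practical reasons, based on the expected rate that participants can be recruited". It supports 30 by the low device risk, bench testing and limited validation, with no power or precision calculation. Section 9.3 sets the significance level at 0.01, which "will be used to control the false discovery rate, due to the expected small limiting sample size".

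Section 4.4 says that "the hypothesis for this study is that the HALOS headgear is sufficiently effective for clinical use, and that the risks are understood adequately". Under section 16, "An internal report will be produced detailing the findings from the study in the form of a clinical evaluation".

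The documents do not state null and alternative hypotheses, one- or two-sided testing, an exact or approximate method, a confidence interval, or the result that would count as acceptable performance.

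**The concern.** A test against a reference proportion can be used in two ways. It can try to show that the true rate is above the reference, which would support the effectiveness part of the section 4.4 hypothesis. Or it can look for evidence that the true rate is below it, as a check for poor performance. The plan does not choose, and the choice determines what a result means.

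The reference is close to 1 and the sample is small, so even a perfect result may lie well within what a device exactly at the limit would produce. A strict significance level does not compensate for this. It makes superiority harder to show, and if non-significance is taken as reassurance it makes a poor device easier to pass.

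This is the only analysis specified for the primary outcome, and the findings go into the clinical evaluation report. As written, its author could not say what any result means against the 1-in-50 limit, and could choose direction and method after seeing the data.

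**Working it through.** **Inputs.** Reference p0 = 49/50 = 0.98 (section 9.1); level 0.01 (section 9.3); n = 30 (section 9.2). The number analysed is taken as 30 because section 6.5 replaces withdrawn participants. The plan has no power or sample-size figure to reproduce.

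**1. What a device exactly at the limit produces.** Failures follow a binomial distribution with n = 30 and probability 0.02, so 30 × 0.02 = 0.6 failures are expected.

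- P(30/30) = 0.98^30 = 0.5455
- P(29/30) = 30 × 0.02 × 0.98^29 = 0.3340
- P(28/30 or fewer) = 1 − 0.5455 − 0.3340 = 0.1205
- P(27/30 or fewer) = 0.0217
- P(26/30 or fewer) = 0.0029

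**2. Direction: better than 98%.** The most favourable result is 30/30.

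- Exact one-sided p = 0.545; exact two-sided p = 1.00.
- Uncorrected z-test: standard error = √(0.98 × 0.02 / 30) = 0.02556; z = (1 − 0.98)/0.02556 = 0.78; one-sided p = 0.217.

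Neither approaches 0.01, so power is zero at every true rate. The number of consecutive successes needed is ln(0.01)/ln(0.98) = 227.9, that is 228 (149 at the 0.05 level). Conversely, the highest reference that 30/30 could reject at one-sided 0.01 is 0.01^(1/30) = 0.858.

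**3. Direction: worse than 98%.** From step 1, the exact test at 0.01 rejects at 4 or more failures (p = 0.0029) and not at 3 (p = 0.0217). At 0.05 it rejects at 3 or more. The table gives the chance of no rejection for assumed true failure rates, which the documents do not supply.

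| True failure rate | Exact, 0.01 (3 or fewer failures) | Exact, 0.05, or uncorrected z, 0.01 (2 or fewer) |
|---|---|---|
| 5% | 93.9% | 81.2% |
| 10% | 64.7% | 41.1% |
| 15% | 32.2% | 15.1% |
| 20% | 12.3% | 4.4% |

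If non-rejection were taken as acceptable, the 0.01 level would be the more lenient of the two.

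**4. Effect of method.** At 27/30, z = (0.90 − 0.98)/0.02556 = −3.13. With a continuity correction of 1/60, |z| = (0.08 − 0.0167)/0.02556 = 2.48.

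| Test at 27/30 | p | Reject at 0.01? |
|---|---|---|
| Exact, one-sided | 0.0217 | No |
| z, uncorrected, one-sided | 0.0009 | Yes |
| z, corrected, one-sided | 0.0066 | Yes |
| z, corrected, two-sided | 0.013 | No |

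With 0.6 expected failures the normal approximation is unreliable, and the decision turns on choices the plan leaves open.

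**5. What 30 participants can show.** Exact (Clopper-Pearson) lower limits:

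| Result | One-sided 99% | Two-sided 95% |
|---|---|---|
| 30/30 | 85.8% | 88.4% |
| 29/30 | 79.8% | 82.8% |

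**The case against.** The plan never claims that it will show performance above 98%. A shortfall check is an equally natural reading of section 9.1, and on that reading the test does some work: the exact test at 0.01 would reject a device with a 20% failure rate 87.7% of the time (100 − 12.3) and one with 15% failures 67.8% of the time (100 − 32.2). The statement that 3 failures would pass depends on a reading of non-significance that the plan does not make. This is a development study of a low-risk device, section 9.2 is open about the practical limit, and nothing makes the p-value the sole gate to clinical use. The observed proportion is already the outcome measure and would presumably be reported.

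Much of this stands. The test can flag gross failure, and keeping it for that purpose is reasonable. The shortfall argument is conditional. The second part of the section 4.4 hypothesis, on understanding of risks, is unaffected.

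It does not answer the main point. A check that detects gross failure does not show that a 2% limit is met, and the plan does not say the test is only such a check. The grounds in section 9.2 explain why 30 was chosen, not what 30 tests can establish about 98%. A practical limit on recruitment argues for estimation rather than for a formal test whose interpretation is undefined.

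**Conclusion.** The concern holds. At n = 30 no result can demonstrate a success rate above 98% at the 0.01 level (best exact p = 0.545). In the other direction, non-significance is compatible with failure rates several times the limit: assumed true rates of 5% and 10% go unrejected 93.9% and 64.7% of the time with the exact test. The only specified primary analysis therefore cannot support the effectiveness part of the hypothesis, and its direction, method and interpretation are missing.

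The zero-power result rests only on the plan's own figures, with 30 analysed, and does not depend on sidedness or on exact versus normal methods. The non-rejection percentages depend on the assumed failure rates and on the exact test. This should be corrected before results are known, because a decision rule chosen afterwards would not be credible.

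**What to change.** 1. **Section 9.1:** make the primary analysis the observed proportion with an exact Clopper-Pearson interval, and state what 30 participants can show, using the limits in step 5 of the working.
2. **Section 9.3:** fix the interval level in advance. Either use a one-sided 99% lower bound, which keeps 0.01, or a two-sided 95% interval, with section 9.3 amended to say that 0.01 does not apply to it.
3. **Sections 4.4 and 9.1:** state that the study estimates performance, cannot confirm the 1-in-50 limit, and that a non-significant test will not be read as meeting it.
4. **If a comparison with 0.98 is kept:** define it as an exact one-sided shortfall check used only to flag poor performance, with the rejection count written in (4 or more failures at 0.01, or 3 or more at 0.05).

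The cost is a protocol amendment to sections 4.4, 9.1 and 9.3, with no extra participants or procedures. The claim becomes more modest: after a perfect 30/30 the lower limit is about 86% or 88%, depending on the level chosen, and it is lower with any failure. Keeping a superiority claim instead would need at least 228 participants, all successes.
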